Statistical analyses will be performed using SAS® software version 9.4 or higher. MedDRA version 23.1 will be used for the coding of Medical History and Adverse Events. AEs are graded using Common Terminology Criteria for Adverse Events (CTCAE) Version 5.0. World Health Organization Drug Dictionary (WHO-DD) version

Regeneron Pharmaceuticals Inc. / Protocol: CMP-001-007
IQVIA Biotech (Confidential) Project # SZA56629

B3 Global September 2020 (or later) will be used to code the Prior and Concomitant Medications, and Prior Cancer Systemic Treatments.

A. Data Sources

Data are recorded on electronic case report forms (eCRFs). Central laboratory data will be provided via electronic data transfers. Protocol Section 11 and the study Data Management Plan provide additional details regarding data recording and handling.

B. Definition of Baseline and Study Day

Baseline is defined as the last non-missing observation prior to the first administration of study drugs (CMP-001 or Pembrolizumab). Study Day 1 will be designated as the first day a subject receives either study drug (i.e., Week 1 Day 1).

C. Missing Data

Unless stated otherwise, missing data will not be replaced with imputed values. When relevant, sections below will address how missing data will be handled for the analyses.

Missing or Partial Death Dates

A death date missing the month and day will be imputed as Jan 1st of the year or the date after the date of last known alive, whichever comes last.

A death date missing the day will be imputed as the 1st of the month or the day after the date of last contact, whichever comes last.

Missing Dates in Adverse Events/Concomitant Medications

Every effort will be made to avoid missing/partial dates in on-study data including AE and medication start and stop dates.

Start dates of AEs/ Concomitant medications will be imputed as follows:

- Completely missing start date will not be imputed.
- Start date missing both the month and day will be imputed as:
 - The date of the first dose if the year of the start date is the same as the date of first dose.
 - Otherwise, Jan 1st of the year of the start date will be used.
- Start date missing the day will be imputed as:

Regeneron Pharmaceuticals Inc. / Protocol: CMP-001-007
IQVIA Biotech (Confidential) Project # SZA56629

- The date of first dose if the year and month of the start date are the same as the date of first dose.
- Otherwise, the 1st of the month of the start date will be used.

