Stop dates of AEs / Concomitant Medications will be imputed as follows:

- Completely missing stop date will not be imputed.
- Stop date missing both the month and day will be imputed as Dec 31st of the year of stop date.
- Stop date missing the day will be imputed as the last date of the month of the stop date.
- After imputation, the imputed date will be compared against the date of death, if available. If the planned imputed date is later than the date of death, the date of death will be used as the imputed date instead. If there is no date of death in the EDC for a subject and the planned imputed date is later than the End-of-Treatment (the last drug received) date + 30 days, then the End-of-Treatment (EOT of the last study drug received) date + 30 days will be used for the stop date.

Missing Dates in Prior Medications

Start or Stop dates of Prior Medications will be imputed as follows:

- Completely missing start or stop date will not be imputed.
- Start or stop date with missing both the month and day will be imputed as Dec 31st of the year of stop date.
- Start date missing the day will be imputed as the 1st of the month of the start date.
- Stop date missing the day will be imputed as the last date of the month of the stop date or the study first dose date, whichever comes earlier.

D. Multiple Study Centers

No adjustment for study center is planned.

E. Covariate Adjustment in Primary Analysis

No covariate adjustments are planned.

F. Sample Size Reassessment

Not applicable.

Regeneron Pharmaceuticals Inc. / Protocol: CMP-001-007
IQVIA Biotech (Confidential) Project # SZA56629

G. Ad-hoc Analyses

There will be an ad-hoc analysis planned with the trigger event being two disease assessments after the enrollment of the last subject. The ad-hoc analysis of the endpoints will follow the efficacy analysis methods described in Section **Error! Reference source not found.** below as well as the safety analysis methods detailed in Section **Error! Reference source not found.** below for the exploratory Phase 2 study.

The following unblinded subject information, efficacy-related and safety-related data displays will be produced for the purpose of the ad-hoc analysis. Unless stated otherwise, these displays are summary tables that summarize data for the corresponding analysis set:

- Subject information
 - Demographics
 - Baseline characteristics
 - Disposition
 - Medical history
 - Cancer history
 - ECOG
- Efficacy

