Detailed information on the physical examinations (height, weight, and BMI) will be listed by subject. Clinically significant post-baseline physical examination findings will be reported as AEs.

G. Prior and Concomitant Medications

All medications administered to the subject from 30 days prior to first dose of study treatment (W1D1) until 30 days after discontinuation of both CMP-001 and Pembrolizumab will be recorded in the EDC. Treatment medications for AEs related to study treatment that occur more than 30 days after the last dose of study treatment will also be collected.

Documentation for each medication will include the generic name of the medication, dose per administration, route of administration, dates of administration, and indication for use. Combination drugs must be listed separately by each component study treatment and dose, when possible. Prior cancer treatments will be recorded separately.

Prior medications are those taken within 30 days of the first dose of study treatment and discontinued before the first dose of study treatment.

Concomitant medications are defined as medications which are taken during study treatment and within 30 days of the last dose of study treatment. Additionally, medications started prior to the first dose of study treatment, but with a stop date after the first dose of study treatment and within 30 days of the last dose of study treatment will be considered concomitant medications.

Medications will be coded using the B3 Global September 2020 of World Health Organization drug dictionary and summarized according to the Anatomical Therapeutic Chemical (ATC) class II and preferred term for subjects in the Treated Analysis Set. Subjects will be counted only once for a given concomitant medication for each Anatomical Therapeutic Chemical class and preferred term in the summary tables.

Regeneron Pharmaceuticals Inc. / Protocol: CMP-001-007
IQVIA Biotech (Confidential) Project # SZA56629

Prior and Concomitant medications will be presented in a by-subject data listing. The listing will contain both prior and concomitant medications with an indication of whether the medication is a prior or concomitant medication. The listing will display entries from the Concomitant Medications form, ordered within subject by the “Start Date of Medication”.

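### Year-only prior-medication dates are imputed to 31 December of the stop year, which can put the start after the stop and the stop after first dose

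*SAP*

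**What the plan says.** SAP section VI.C (Missing Data) has a block headed Missing Dates in Prior Medications. Its rules are:

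- Date wholly missing: "Completely missing start or stop date will not be imputed".
- Month and day missing, start and stop together: "Start or stop date with missing both the month and day will be imputed as Dec 31st of the year of stop date".
- Start missing only the day: "Start date missing the day will be imputed as the 1st of the month of the start date".
- Stop missing only the day: the last day of the stop month "or the study first dose date, whichever comes earlier".

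The block just above it covers adverse events and concomitant medications. There, a year-only start becomes the first dose date if the years match. If they do not: "Otherwise, Jan 1st of the year of the start date will be used". That block also ends with a check on imputed stop dates: "If the planned imputed date is later than the date of death, the date of death will be used as the imputed date instead". Where no death is recorded, the limit is end of treatment plus 30 days.

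SAP section IX.G gives the definition: "Prior medications are those taken within 30 days of the first dose of study treatment and discontinued before the first dose of study treatment". A medication begun before first dose counts as concomitant if it stopped after first dose and within 30 days of the last dose. Section IX.G asks for a summary table by ATC class and preferred term, and for a listing that flags each entry as prior or concomitant. Section VI.G puts prior and concomitant medications in the ad-hoc analysis package.

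**The concern.** The year-only bullet has two separate faults.

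**Start date.** It is taken from the stop year and set to that year's last day. The neighbouring start rules use the start date itself and choose an early day. The result can be a start later than a known stop.

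**Stop date.** It is set to 31 December with no cap at first dose, although the bullet for a missing day has one. A drug that ended before first dose in the same calendar year is then dated as ending after it, contrary to the SAP's own definition of a prior medication.

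At stake are impossible derived dates in the listings and, under some conditions, the wrong prior/concomitant status in the medication outputs.

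**Working it through.** The plan states no figure for this rule, so there is nothing to reproduce. The check applies the rule literally. The calendar dates are illustrative assumptions in 365-day years.

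**1. Year-only start, complete stop.** Imputed start = 31 December of the stop year.

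- The imputed start is later than the stop unless the stop is itself 31 December, so on 365 − 1 = 364 of 365 possible stop days.
- Example: start 2019, stop 10 February 2022 (day 41). The imputed start is 31 December 2022 (day 365), which is 365 − 41 = 324 days after the stop.
- The largest gap is 365 − 1 = 364 days, for a stop on 1 January.
- If the stop is wholly missing it is not imputed, so the rule has no year to use. If both dates are year-only, they fall on the same day.

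**2. Year-only stop in the year of first dose.** Imputed stop = 31 December of that year.

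- It is later than first dose on 364 of 365 possible first-dose days, and equal to first dose on the other.
- Example: first dose 15 March 2022 (day 74), stop recorded as 2022. The imputed stop is 365 − 74 = 291 days after first dose.

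**3. Year-only stop in an earlier year.** The imputed stop reaches first dose in 0 of 365 cases, so nothing goes wrong. This case is narrow, though. A prior medication must have been taken within 30 days of first dose, and 31 December + 30 days = 30 January. A stop in the preceding calendar year therefore qualifies only for first doses up to about 30 January.

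**4. What becomes of the example in step 2.** Take a drug begun before first dose and apply the sentence of section IX.G written for such drugs. The imputed stop must be no later than last dose + 30 days, and 31 December 2022 − 30 days = 1 December 2022.

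| Flag set | Last dose | Result |
|---|---|---|
| After imputation | 1 December 2022 or later | Concomitant |
| After imputation | Before 1 December 2022 | Neither definition met |
| Before imputation | Any | Prior, with a stop 291 days after first dose |

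The first row needs a last dose at least 335 − 74 = 261 days (about 37 weeks) after first dose.

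**5. Whether another rule repairs it.** The check against death or end of treatment plus 30 days is written for adverse-event and concomitant stop dates. It does not cap at first dose, and it does not compare start with stop. Section I.B says the SAP prevails over the protocol, so the protocol does not correct the rule either.

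**6. The existing day-missing cap.** With first dose 15 March 2022 and a stop of March 2022, the rule gives the earlier of 31 March and 15 March, which is 15 March. A stop on the first-dose date is neither before first dose (prior) nor after it (carried over as concomitant). That cap is one day too late for the definition.

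**The case against.** A reader might infer that the rule always turns prior medications into concomitant ones. The documents do not support that. The bullet sits under a heading for prior medications, so it can be read as applying to records already classed as prior. On that order no record changes class, and the only damage is an inconsistent stop date. On the other order, reclassification also depends on the last dose date. The SAP does not say which order applies. This part of the objection stands, and the consequence has to be stated conditionally.

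It can also be said that a stop recorded only as 2022 does not show that the drug ended before a March 2022 first dose, and that counting an uncertain drug as concomitant is defensible. That stands too. The stop-date fault is clear only for records known on other grounds to be prior. But the SAP does not present the missing cap as a cautious choice, and its day-missing rule goes the other way.

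Finally, a wrong start does not change prior status when the stop is complete, and the table counts subjects rather than durations. This is correct. The start fault yields impossible dates, not misclassification. It is still a stated rule that gives a wrong result.

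**Conclusion.** The rule is wrong as written, and the matter is minor. The start-date fault needs no assumption beyond a literal reading: 364 of 365 complete stop dates precede the imputed start. The stop-date fault arises when the year-only stop falls in the year of first dose. Its effect on classification rests on the unstated order of flagging and imputation, on the last dose date, and on reading section IX.G by its sentence for drugs begun before first dose. A looser reading of that section's general sentence could count the record as concomitant whatever the last dose date.

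Only the medication table and listings, including their place in the ad-hoc package, are touched. ORR, DOR, PFS and OS do not use these dates. The documents do not say how many records have year-only dates. With 24 treated subjects and descriptive analyses, there may be few. The bullet may be two rules merged by a drafting slip, but nothing else in the SAP corrects it.

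**What to change.** Replace the single bullet in SAP section VI.C with separate rules:

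- **Start missing month and day:** 1 January of the start year. In the example this gives 1 January 2019, before the stop of 10 February 2022.
- **Stop missing month and day, record known to be prior:** the earlier of 31 December of the stop year and the day before first dose. In the example this gives 14 March 2022, which meets the definition of prior.
- **Stop missing only the day:** move the existing cap from the first dose date to the day before it.
- **Order:** assign the prior/concomitant flag before imputing, and say what information sets it when the stop date is partial.

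Capping the year-only stop at the first dose date itself would not be enough, for the reason in step 6 of the working. The cost is a few lines of SAP text and the matching code, with no new data and no effect on efficacy outputs.

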7.1.1. Informed Consent

Subjects must sign a written informed consent form (ICF) before the initiation of any study procedures and thereafter if there are any ICF changes. Subjects will be given a signed copy of the ICF to take home. Subjects unable to provide written informed consent on their own behalf will not be eligible for the study.

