12.3. Written Informed Consent

The ICF should be written in accordance with the current revision of the Declaration of Helsinki and current ICH and GCP guidelines. The Sponsor or its representatives will provide template ICF to the Investigator. The final ICF must be approved by the Sponsor or representatives before being reviewed and approved by the IRB. The final IRB approved ICFs must be provided to the Sponsor or its representatives for regulatory purposes.

The Investigator will ensure that the subject is given full and adequate oral and written information about the nature, purpose, possible risk, and benefit of the study. Subjects must also be notified that they are free to discontinue from the study at any time. The subject

should be given the opportunity to ask questions and allowed time to consider the information provided.

Each subject must provide voluntary written informed consent (and sign other locally required documents) according to local requirements after the nature of the study has been fully explained. Each subject must sign an ICF before any study-related activities are performed and before participation in the study. A copy of the signed ICF must be provided to the subject, and the original signed ICF must remain in each subject's study file and must be available for verification by the study monitor at any time. The Investigator will also ensure each subject follows the proper re-consenting procedures for all applicable or additional versions of the ICF that become effective while they are enrolled in the study.

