Per Sponsor's decision, site activation and study enrollment were stopped earlier for any subjects who had not signed informed consent yet, and analyses were made exploratory. Consequently, the SAP will not necessarily be consistent with the protocol. In case of any discrepancies, this SAP will govern the analysis of data from this study.

II. Study Design

A. Design Overview

This is a multicenter, open-label, exploratory Phase 2 clinical trial of CMP-001 IT in combination with pembrolizumab IV in subjects with recurrent or metastatic HNSCC. Eligible subjects must have histologically- or cytologically-confirmed recurrent or metastatic HNSCC considered incurable by local therapies. All subjects will receive CMP-001 IT and pembrolizumab IV according to the treatment schedule until a reason for treatment discontinuation is reached.

CMP-001 10 mg will be administered weekly for 7 doses, after which it will be administered Q3W until the subject meets a condition for discontinuation of study treatment. The treatment will be given for a maximum of 2 years from the start of the study treatment. The first dose of CMP-001 may be administered SC or by IT injection, at the discretion of the Investigator; all subsequent doses are planned to be administered IT. The initial 7 CMP-001 doses on a weekly schedule must be completed before moving on to the Q3W CMP-001 dosing schedule.

If all injectable tumors regress, CMP-001 may be injected SC in the region of prior tumors or draining lymph node bed, at the Investigator's discretion (see Protocol Appendix F). On visits where both study drugs are administered, CMP-001 IT should be administered before pembrolizumab. CMP-001 should be administered until a reason for treatment discontinuation is reached, or for a maximum of 2 years from the start of the study treatment. See Protocol Section 5.1.2.4 for treatment modifications for CMP-001. Pembrolizumab 200 mg IV will be administered following CMP-001 10 mg IT injection at W1D1 and Q3W thereafter according to the KEYTRUDA® USPI. Pembrolizumab treatment during this study will continue until the subject meets a condition for discontinuation of study treatment.

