 - ORR, DOR, TTR, PFS per RECIST v1.1 by Investigator
 - OS
 - Selected subgroup analysis
- Safety
 - Study drug exposure: CMP-001 and pembrolizumab
 - Prior and concomitant medications
 - Prior and concomitant procedures
 - All TEAEs (SAE, AESI)
 - Summary of clinical laboratory results
 - Summary of ECG results

H. Multiple Comparisons

No control for the effect of multiple comparisons is planned.

I. Analysis Sets

Three analysis sets will be defined for use with various analyses. The following table illustrates the relationship between each population and the analyses for which the data from the population will be used.

Regeneron Pharmaceuticals Inc. / Protocol: CMP-001-007
 IQVIA Biotech (Confidential) Project # SZA56629

Analysis Set	Analysis					
	Baseline	Subject Disposition	Efficacy	Safety	PD	Tumor Biopsy
Treated	X	X	X	X		
Pharmacodynamic					X	X
All Screened		X				

1. Treated Analysis Set

The Treated Analysis Set is defined as all subjects who receive at least 1 dose of study treatment.

2. Pharmacodynamic Analysis Set

The Pharmacodynamic Analysis Set is defined as all subjects who receive at least 1 dose of CMP-001 and have at least 1 measurable sample at Baseline and at least 1 evaluable biomarker sample after CMP-001 administration.

3. All-Screened Analysis Set

The All-Screened Analysis Set is defined as all subjects who was screened including subjects who were screen failure.

J. Subgroups of Analysis Populations

1. HPV Status

- Negative
- Positive

2. PD-L1 Expression (Combined Positive Score, CPS)

- $1 \leq \text{CPS} < 20$
- $\text{CPS} \geq 20$

3. Schedule

- A: Subjects under Schedule A are those who consented to protocol v1.0 and v2.0.
 - Per Protocol, subjects will receive CMP-001 10 mg weekly for 7 doses, after which CMP-001 will be administered every 3 weeks (Q3W), beginning on Week 10 Day 1 (W10D1), then on Week 13 Day 1 (W13D1), etc.
 - Subjects will receive Pembrolizumab 200 mg IV over 30 minutes following CMP-001 injection at Week 1 Day 1 (W1D1) and every 3 weeks thereafter (W4D1, W7D1, etc.) according to the

Regeneron Pharmaceuticals Inc. / Protocol: CMP-001-007
IQVIA Biotech (Confidential) Project # SZA56629

KEYTRUDA® (pembrolizumab) United States Prescribing Information. Pembrolizumab should be administered until the subject satisfies a condition for study treatment discontinuation.

- B: Subjects under Schedule B are those who consented to protocol v3.0, including those who reconsented to v3.0 from v2.0.

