As of the data cutoff date, the number and percentage of subjects who screen fail and enroll in the study (receive at least one dose of study treatment), discontinue study treatment, and discontinue the study will be summarized for all screened subjects. The primary reason for treatment(s) and study discontinuation will also be summarized for Treated Analysis Set. Additionally, subgroup analysis of disposition by schedule will also be performed. Subject disposition will be presented in a by-subject data listing.

Study treatment (CMP-001 only or both CMP-001 and Pembrolizumab) may be discontinued for any of the following occurrences:

- Adverse Event
- PD per RECIST v1.1
- Subject Achieved and Maintained a Confirmed CR or iCR (and has been treated for at least 24 weeks, and has received at least 2 doses of both study treatments beyond the date of initial CR/iCR)
- Upon Request of the Sponsor or Regulatory Agency

Regeneron Pharmaceuticals Inc. / Protocol: CMP-001-007
IQVIA Biotech (Confidential) Project # SZA56629

- Clinical Disease Progression
- Medically Necessary in the Opinion of the Investigator
- Subject Withdrew Consent for Treatment
- Subject Became Pregnant or Began Breastfeeding
- Subject Lost to Follow-up
- Death
- Subject Completed 2 Years of Study Treatment
- End of Clinical Trial
- Other

Study Participation may be discontinued for any of the following occurrences:

- Completed
- Adverse Event
- Subject Withdrew Consent
- Lost to Follow-Up
- Death
- Study Terminated by Sponsor
- End of Clinical Trial
- Other

Percentages of subjects who withdrew for each of these reasons will be calculated using all members of the relevant analysis set for the denominator.

C. Protocol Deviations and Population Inclusions

All protocol deviations will be captured electronically outside of the Electronic Data Capture (EDC) system in the IQVIA Biotech IL-2 system and presented in a by-subject data listing. All deviations will be reviewed on an ongoing basis and classified as major or minor following study review process.

VIII. Efficacy Analyses

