The performance of the statistical analysis for the exploratory efficacy endpoint is contingent on the availability of the data source. Given the response assessment based on itRECIST³ by Investigator has not been collected, and that the RECIST v1.1 and iRECIST were deemed sufficient for the purpose of the response assessment in the study from the Medical's perspective, no exploratory efficacy analyses will be carried out for the exploratory phase 2 study.

IX. Safety Analyses

Safety analyses will use data from the Treated Analysis Set. Subjects will be analyzed according to the actual study treatment received.

A. Exposure

Exposure to CMP-001 and Pembrolizumab will be summarized separately for the Treated Analysis Set with descriptive statistics for the number of doses received, the average number of volumes injected per dosing visit, the duration of treatment for each treatment (weeks), the planned dose intensity, the actual dose intensity, the relative dose intensity (%), and the treatment compliance.

1. Duration of Treatment

Regeneron Pharmaceuticals Inc. / Protocol: CMP-001-007
IQVIA Biotech (Confidential) Project # SZA56629

Duration of treatment (DoT) of CMP-001 and Pembrolizumab will be summarized in a descriptive manner, respectively. DoT will be calculated as follows:

$$\text{DoT (weeks)} = [\min(\text{last dose date} + 21 \text{ days, discontinuation/completion date}) - \text{first dose date}] / 7$$

2. Dosing Intensities

(1) Actual dose intensity (mg/week) will be calculated as the total actual cumulative dose received divided by duration of treatment (weeks) for CMP-001 and Pembrolizumab, respectively.

(2) Planned dose intensity (mg/week) will be calculated as the total planned cumulative dose to be received divided by the planned duration of treatment (weeks) based on the protocol schedule.

$$\text{Planned Duration of Treatment (weeks)} = \text{number of planned treatments} \\ * 3 \text{ weeks}$$

(3) Relative dose intensity (%) will be calculated based on the actual cumulative dose received relative to the planned cumulative dose throughout the duration of treatment as follows:

$$\text{Relative dose intensity (\%)} = (\text{actual dose intensity} / \text{planned dose intensity}) * \\ 100\%$$

3. Treatment Compliance

Treatment compliance is calculated as the number of CMP-001/Pembrolizumab doses received/expected doses within the treatment period defined as time from first dose to last dose.

4. Dosage Modifications

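### SAP VI.J.3 sets schedule by consent version without tying it to first dose, so any v2.0 subject who reconsented to v3.0 after W1D1 biases by-schedule OS towards Schedule B

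*SAP*

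**What the plan says.** SAP VI.J.3 forms two schedule subgroups. For A: "Subjects under Schedule A are those who consented to protocol v1.0 and v2.0". For B: "Subjects under Schedule B are those who consented to protocol v3.0, including those who reconsented to v3.0 from v2.0". Neither definition mentions the date of first dose or the doses received.

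The labels are used widely. SAP VIII.C plans ORR, DOR and OS by schedule. SAP VII.B does so for disposition, IX.A for dosing and intensity, IX.B for the AE overview and IX.C for deaths. SAP VIII.A counts OS from first dose of study treatment.

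Reconsent during the study is foreseen. Protocol 7.1.1 has the consent form signed "before the initiation of any study procedures and thereafter if there are any ICF changes". Protocol 12.3 calls for "re-consenting procedures for all applicable or additional versions of the ICF that become effective while they are enrolled in the study", and SAP VII.B describes enrolled subjects as those who "enroll in the study (receive at least one dose of study treatment").

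On dosing, VI.J.3 gives seven weekly CMP-001 doses for A and two for B, each followed by dosing every three weeks. SAP II.A describes only the seven-dose plan: "The initial 7 CMP-001 doses on a weekly schedule must be completed before moving on to the Q3W CMP-001 dosing schedule". SAP IX opens its safety section with "Subjects will be analyzed according to the actual study treatment received". SAP I.B says the SAP prevails over the protocol where they differ, so the VI.J.3 wording decides the tables.

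**The concern.** A label acquired after time zero must not be used to group subjects from time zero. A subject has to be alive to sign a new consent form. For anyone who reconsents after first dose, the interval from first dose to reconsent therefore cannot contain a death, yet it counts as Schedule B survival. The deaths that do occur in that interval among v2.0 starters stay in A. B gains and A loses even if the schedules are equivalent.

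SAP VIII.A adds a route for ORR. Subjects who discontinue because of death before any post-baseline scan are scored as PD, and the first scan is at W10. A v2.0 starter who dies before reconsent is thus a non-responder who can only be in A.

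Protocol 1.3.3 introduces the modified Schedule B into this study because HNSCC injections often need radiology assistance. Readers will naturally compare the two rows.

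A separate question is what a late reconsenter's dosing and safety data represent when tabulated under B.

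**Working it through.** The plan gives no figure for the number or timing of reconsents, so there is nothing of its own to reproduce. What follows gives the time scale, the size per reconsenter, the effect on crude deaths, and the dosing comparison.

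**Time scale (SAP I.B, II.C).** Amendment 1 (v2.0) was approved on 3 Aug 2021 and Amendment 2 (v3.0) on 14 Jan 2022: 164 days, and 164/30.4375 = 5.39 months. The last subject enrolled on 22 Jun 2022, 159 days later. Starts under v2.0 and v3.0 can therefore span 164 + 159 = 323 days. These are approval dates; site activation dates are not given, so 5.4 months is a scale and not a strict bound.

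**OS per reconsenter.** Assume exponential OS with median m. The range 10.7 to 14.9 months comes from Protocol 1.1: 14.9 is pembrolizumab monotherapy and 10.7 is the cetuximab-chemotherapy arm, used here only to bracket. For a subject known alive at t months, S(12 | alive at t) = 2^(-(12 - t)/m).

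| Reconsent at t (months) | m = 10.7 | gain | m = 14.9 | gain |
|---|---|---|---|---|
| 0 | 46.0% | – | 57.2% | – |
| 1 | 49.0% | 3.1 | 59.9% | 2.7 |
| 3 | 55.8% | 9.9 | 65.8% | 8.6 |
| 5.39 | 65.2% | 19.2 | 73.5% | 16.3 |

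The B row rises by (gain) × (share of B who reconsented after W1D1). At an assumed share of 25% that is 0.7 to 4.8 points across the table; at 50%, 1.4 to 9.6. The A row also falls, by an amount that depends on the unknown split of subjects by version.

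**Same effect as a hazard ratio.** A simulation with no schedule effect assumed that half the subjects start under the earlier version, half of those alive at time L reconsent, and everyone has 24 months of follow-up. The labelled B:A hazard ratio was 0.97 (L = 1 week), 0.91 (1 month), 0.78-0.80 (3 months) and 0.67-0.69 (6 months). Counting the time before reconsent in A returned 0.99-1.01.

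**Crude deaths.** Again with no schedule effect, take m = 10.7, equal numbers of v2.0 and v3.0 starters entering uniformly, reconsent at the date of v3.0 approval, and cutoff 18 weeks after last entry (two scan intervals).

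- v2.0 starts spread over the full 164 days, 50% of survivors reconsent: A goes from 54.0% to 60.2%, B from 35.1% to 38.2%. The gap widens from 18.9 to 22.0 points.
- v2.0 starts within 2 months of v3.0, 25% reconsent: A goes from 48.9% to 49.9%, B from 35.1% to 37.1%. The gap narrows from 13.7 to 12.8 points (unrounded difference).

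B's own percentage rises in both cases because v2.0 starters bring longer follow-up.

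**Dosing (VI.J.3).** A is dosed at W1 to W7, W10, W13 and so on; B at W1, W2, W4, W7, W10 and so on. They differ only at W3, W5 and W6. A subject who reconsents after W6D1 has had every dose that distinguishes A and has no later visit that differs, yet is tabulated as B. SAP IX.A.3 divides doses received by expected doses without saying which schedule sets them. After a full A induction to W7, compliance is 7/7 = 100% or 7/4 = 175%.

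**The case against.** The strongest reply is that no reconsent after dosing is documented. The two protocol consent sections are general text, and a subject in the 30-day screening window when v3.0 arrived could have reconsented before W1D1, with no bias at all. That stands: the defect is a missing timing rule, and a reader who concludes that bias has occurred goes beyond the documents. Reconsent within days of W1D1 would also matter little.

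The stakes are limited too. There are 24 treated subjects, everything is descriptive, no test of A against B is planned, and pooled ORR and OS do not use the label. With an assumed 12 subjects per row, 6/12 has an exact 95% interval of 21-79%, far wider than the shifts above. This limits the severity; it does not justify a known artefact.

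Four stronger readings are tempting and are not supported:

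- **Deaths must favour B.** Usually the gap widens through A, but the second deaths scenario shows it can narrow, and B's own percentage can rise.
- **Every later reconsent contradicts SAP IX.** The schedules are identical until W3D1, so an early reconsenter may truly have been dosed as B. Everyone receives the same two drugs, and IX does not say that its sentence covers schedule.
- **The two groups overlap.** The explicit inclusion of reconsenters in B settles where they go.
- **Relative dose intensity is distorted for each reconsenter.** IX.A.2 sets planned duration at three weeks per planned treatment under either schedule, so a subject's own value does not change with the label.

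**Conclusion.** The concern holds conditionally and centres on by-schedule OS. If any subject reconsented to v3.0 after W1D1, the VI.J.3 label credits guaranteed survival to B. The gain in 12-month OS is about 3 points per reconsenter at 1 month, 9-10 at 3 months and 16-19 at 5.4 months, times the unknown share of B they make up. This assumes exponential OS with a median of 10.7 to 14.9 months. If all reconsents came first, the bias is zero.

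By-schedule ORR can lean the same way through survival alone; its size is not computed. Crude deaths by schedule are distorted, usually by raising A's percentage, without a certain direction.

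Separately, the SAP leaves unstated whether actual treatment received refers to schedule and which schedule sets expected doses. II.A describes only seven weekly doses, while VI.J.3 and Protocol 5.1.2 describe two weekly doses for v3.0. These texts must be reconciled.

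This should be fixed before the subgroup tables are read, but it does not threaten the primary result.

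**What to change.** In VI.J.3, for by-schedule efficacy and deaths, define schedule as the latest protocol version consented to on or before the W1D1 dose: v1.0 or v2.0 is A, v3.0 is B, and later reconsent does not change the group. Flag later reconsenters, report how many reconsented before and after W1D1, and show follow-up time from first dose beside by-schedule deaths.

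In IX, state how actual treatment received applies to schedule in the by-schedule exposure and AE tables. Count expected doses by the version in force for that subject at each visit. Reconcile II.A with VI.J.3.

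The cost is one definition, a short statement in IX and one derived flag. Consent date and each CMP-001 dose date are already to be listed (VII.A, IX.A); the sponsor must confirm that every reconsent date is captured. The B subgroup may become smaller. Subjects who reconsent between W1D1 and W3D1 would be counted in A for efficacy although they may have been dosed as B. If A set their expected doses, four doses to W7 would show as 4/7 = 57% compliance, which is why the exposure rule must be stated separately. If no reconsent followed W1D1, the change alters no result and puts that fact on record.
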